9.4 STUDY WITHDRAWAL CRITERIA

Patients will be withdrawn from the study if any of the following occurs;

- Patient withdraws consent
- Death

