11.2.2 TREATMENT DISCONTINUATION

Patients will be discontinued from the study treatment if any of the following occurs as noted in Section [9.5](#).

- Disease progression based on RECISTv1.1
- An inter-concurrent illness that prevents further administration of NOX66
- An adverse event that is intolerable to continue the treatment with NOX66 and doxorubicin or any DLT (Section [8.3](#)) that has not resolved to Grade 1.
- Any other reason the Investigator considered that impacts the patient's safety.

For the patients who discontinue treatment, they will continue on study for follow-up visits for tumor evaluation. All anti-cancer treatments should be recorded in the eCRF. In those patients who have evidence of disease progression during the combination of NOX66 and doxorubicin, additional tumor evaluation assessments are not needed.

If a patient is withdrawn from the study at any time, either at his/her request or at the Investigator's discretion, regardless of the reason, the Investigator will record on the relevant page of the eCRF the reason(s) for withdrawal and the day of last dosing. The eCRF (and the clinical study report) will include reasons for patient withdrawals, as well as other details relevant to the patient's withdrawal.

Any patient who appears to be noncompliant from Cycles 2 to 6 should be counselled but not withdrawn from the study. Patients who discontinue for non-safety related reasons or for noncompliance prior to the end of Cycle 1 in the Dose-Escalation Part can be replaced.

Should any patient withdraw or be withdrawn from the study prior to the completion of the Month 18 follow-up visit, every effort should be made to complete the assessments at the End of Study (Section [11.6.2.12](#)). Patients experiencing adverse events should be followed until the AE has resolved, stabilized, or is no longer deemed clinically significant, as judged by the Investigator. Appropriate supportive and/or definitive therapy will be administered as required.

Discontinuation due to treatment failure, as defined by disease progression, is to be expected since doxorubicin is not curative for sarcoma and the optimal dose and dose frequency is not known for NOX66. Alternate treatments for sarcoma may be offered to the patient.

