11.6.2.12 Month 18 (from Cycle 1 Day 1) - End of Study/Early Termination

- Assess tumor response with CT or MRI, including patients who discontinue the study for progressive disease.
- Measure vital signs (blood pressure, pulse [radial or brachial (to be measured over 30 seconds if performed manually)], respiration rate and body temperature [oral or aural]; Section 11.4.2.1).
- Assess ECOG performance status.
- Collect urine and fasting blood samples for clinical laboratory tests (Section 11.4.2.4).
- Administer questionnaires BPI-SF, EORTC QLQ-C30 and EORTC QLQ-FA12.
- Perform a physical examination (Section 11.4.2.2).
- Review and record concomitant medications.
- Assess and review TEAEs (Section 16).
- Assess overall survival.

Table 4 Schedule of Procedures and Assessments for Three Periods of the Study

Procedure/Assessment	Study Day	Dose Escalation & Dose Expansion	Dose Escalation NOX66 Monotherapy Period							
		Screening	Monotherapy (Days)							Off-treatment Days
		Day -28 to Day -1	1	2	3	4	5	6	7	8
Obtain informed consent		X								
Inclusion/exclusion criteria		X	X							
Medical and surgical history ¹ (including histopathology data and STS grade)		X	X							
Assess disease status (CT and/or MRI) ²		X								X
Vital signs ³		X	X						X	
Physical examination ⁴		X	X						X	
ECOG performance status		X							X	
Hematology, clinical chemistry ⁵		X	X						X	
Urine pregnancy test (WOCBP only)		X	X							
BNP, troponin I			X						X	
Blood for cytokines, chemokines, immunoassays (ENOX2)		X [†]	X [†]						X	
Genetic mutation sample		X [†]	X [†]							
Archival tissue sample (Optional)		X								
Urinalysis		X	X						X	
12-lead ECG ⁶		X	X						X	
Holter monitoring ⁶									X	
Dispense 7-day supply of NOX66			X							
Echocardiography		X								
Administer NOX66 ⁷			X	X	X	X	X	X		
PK samples ⁸			X	X					X	X
Record AEs		X						X		
Prior & concomitant medications		X						X		
Assess dosing compliance ⁹									X	
Brief Pain Inventory (BPI-SF) ¹⁰			X						X	
EORTC QLQ-C30 ¹⁰			X							
EORTC QLQ-FA12 ¹⁰			X						X	
Suppository Acceptance Questionnaire ^{10, 19}								X		

Procedure/Assessment Study Day	Dose Escalation and Dose Expansion Combination of Doxorubicin and NOX66 Treatment Period Cycles 1 - 3																
	Cycle 1 ¹						Cycle 2					Cycle 3					
	1	2	3-7	8	9 & 16	21	1	2	3-7	9 & 16	21	1	2	3-7	8	9 & 16	21
Assess disease status (CT and/or MRI) ²											X						
Vital signs		X						X					X				
Physical examination	X						X					X					

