11. The additional tests for hematology and serum chemistry on Days 9 and 16 are to assess any hematological or clinical laboratory tests for DLTs and/or require a dose reduction to 60 mg/m^2 or lower (37.5 mg/m^2 or 18.75 mg/m^2 based on serum bilirubin), or a delay in initiation of another cycle of the combination. These additional hematological and clinical laboratory tests should be performed at each cycle. Visit windows are ± 2 days of the scheduled visit.
12. During combination treatment cycles, NOX66 is administered on Days 1 to 7 and doxorubicin is administered on Day 2.
13. Doxorubicin (75 mg/m^2 or reduced dose) to be given on Day 2 of each 21-day cycle.
14. For Dose-Escalation Cohorts, PK samples will be obtained at pre-dose and at 1 and 2 hours post NOX66 on Day 2 Cycle 1. PK samples for idronoxil will be obtained on Day 2 of Cycles 2, 4 and 6 at pre-dose and 4 hours post dose. Additional PK samples for idronoxil will also be obtained pre-dose on Day 7 and at 8 or 12 hours after the last dose of NOX66 on Day 7 for those on a TID or BID regimens, respectively on Cycles 1, 3, and 5. For the Dose Expansion Cohort, PK samples for idronoxil will be obtained on Day 2 of Cycles 1, 2, 4, and 6 at pre-dose and at 4 hours post NOX66 and on Cycle 1 at 6 hours post NOX66. On Cycles 1, 3, and 5 PK samples are to be collected just prior to the morning dose of NOX66 on Day 7. For doxorubicin in the Dose Escalation Cohort, PK samples will be obtained at 0.5, 4 and 6 hours after the end of infusion on Day 2 Cycle 1 and at 0.5 and 4 hours at the end of infusion on Day 2, Cycles 2, 4 and 6. For doxorubicin in the Dose Expansion Cohort, PK samples will be obtained at 0.5, 4 and 6 hours after the end of infusion on Day 2 Cycle 1 and at 0.5 and 4 hours at the end of infusion on Day 2, Cycles 2, 4 and 6 ([Table 7](#)).
15. All patients who discontinue the study early for whatever reason after the first dose of NOX66, or during treatment cycles (Cycles 1-6), will be followed up within 28 days of discontinuation and submit to assessments detailed in the column of Cycle 6 Day 21/Early Termination. Patients who discontinue the study early during the follow-up period will complete a final visit with assessments detailed in the column of End of Study/Early Termination. Patients who complete the study in full will have an End of Study visit at Month 18.
16. Adverse events to be recorded up to 30 days after the last dose of NOX66 or doxorubicin, whichever is longer.

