14.3.10 EFFICACY ANALYSES

Treatment response will be assessed by RECIST v1.1 criteria for patients in the FAS at the end of Cycles 2, 4, and 6, at the 6-month, 9-month, and 12-month follow-up visits, and at the End of Study or Early Termination. Along with CR, PR and SD, the ORR will be defined as the relative frequency of patients with either CR or PR, and the DCR will be defined as the relative frequency of patients with CR, PR, or SD.

The ORR, the DCR, and the frequencies of CR, PR, SD, and PD will be summarized at the end of Cycles 2, 4 and 6 and at the 6-month, 9-month, 12-month and up to 18-month follow-up visits. A summary will also be provided of best response on study.

At the assessment at the end of Cycle 6, a one-sided exact binomial test will be used to test the null hypothesis that the ORR is no greater than 0.20 (20%) against the alternative hypothesis that the ORR is greater than 0.20 at an approximate level $p = 0.025$. A similar test against the performance level of 0.20 will be performed for the rate of best objective response on study.

Overall survival will be defined as the time in months from initial treatment until death or censoring. Patients not known to have died at the time of analysis will be censored at the time of last contact with study personnel., including patients who are lost to follow-up. The overall survival curve will be estimated for the FAS by the Kaplan-Meier method.

Progression-free survival will be defined as the time in months from initial treatment until death, disease progression, or censoring. Patients who are lost to follow-up will be censored at the time of their last contact with study personnel. Patients who leave the study to begin an alternative therapy will be censored on their day of study discontinuation. The PFS curve will be estimated for the FAS by the Kaplan-Meier method.

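### Two passages word progression and new therapy as study exits while the rest of the protocol keeps such patients in follow-up; any progressor handled as an exit may have a later death missed, biasing overall survival upward

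*Combined protocol and SAP*

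**What the plan says.** **Text under which follow-up continues**
- Section 9.4 ("Patients will be withdrawn from the study if any of the following occurs") lists two events: consent withdrawal and death.
- Section 9.5 makes RECIST progression a reason to withdraw treatment.
- Section 11.2.2 says: "For the patients who discontinue treatment, they will continue on study for follow-up visits for tumor evaluation".
- The Table 2 note allows other sarcoma medication during follow-up.
- Section 8.1.2 follows all patients for PFS and OS. Table 4 schedules survival status at Months 6, 9, 12, 15 and 18, and Month 15 is by telephone or chart review.

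**Text that words the same events as study exits**
- Section 11.6.2.12 asks for Month 18 / Early Termination imaging, "including patients who discontinue the study for progressive disease".
- Section 14.3.10, in the PFS paragraph, says: "Patients who leave the study to begin an alternative therapy will be censored on their day of study discontinuation".
- Section 11.2.2 also mentions withdrawal from the study at the Investigator's discretion, a route that Section 9.4 does not list.

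**What follows an exit**
- Table 4 footnote 15 covers "All patients who discontinue the study early for whatever reason after the first dose of NOX66" or during the treatment cycles. It gives them follow-up within 28 days with the Early Termination assessments and states no survival contact after that.
- Section 14.3.10 sets the OS rule: "Patients not known to have died at the time of analysis will be censored at the time of last contact with study personnel".

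**The concern.** Whether a progressor stays under survival follow-up depends on which passage a site applies. A site could reasonably read progression as an exit. The only purpose that Section 11.2.2 gives for staying on study after treatment stops is tumor evaluation. It then says that for patients who progress on the combination "additional tumor evaluation assessments are not needed", and it does not mention survival contact for them.

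If such a patient is closed out, last contact falls soon after progression and OS is censored there. That censoring is informative, because the risk of death is higher after progression than before it. The patients left in the risk set are then disproportionately progression-free, and the Kaplan-Meier curve sits too high. The study has no control arm, so a reader of the OS median would have only outside figures to set it against, such as the doxorubicin medians in Section 6.1. Contacts that were never made may not be recoverable at analysis.

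**Working it through.** The plan gives no OS assumption or power, so there is no figure of its own to reproduce. The check asks which way the bias goes and how large it is for a given share of progressors treated as exits.

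**Inputs from the documents**
- Median PFS 4.6 and median OS 12.8 months on doxorubicin alone (Section 6.1, the 455-patient study).
- Month 18 as the end of follow-up (Table 2).
- Up to 34 patients (Section 14.1).

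**Assumptions not in the documents**
- Constant hazards.
- A fraction f = 10% or 20% of PFS events are deaths without progression.
- Exiting progressors have their last contact 28 days (0.92 months) after progression.
- Later deaths among exiting patients are not learned of.
- The share e of progressors who exit is varied from 0 to 100%.

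**Hazards per month**
- PFS event: h = ln 2 / 4.6 = 0.1507.
- Death before progression: d = f x h = 0.0151 (f = 10%) or 0.0301 (f = 20%).
- Progression: p = (1 - f) x h = 0.1356 or 0.1205.
- Death after progression, q, is set so that S(12.8) = 0.5, where S(t) = exp(-ht) + p[exp(-qt) - exp(-ht)]/(h - q). This gives q = 0.1002 or 0.0838.
- Check for f = 10%: 0.145 + 2.685 x (0.277 - 0.145) = 0.50.
- True 12-month OS is then 53.1% or 52.8%.

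**What Kaplan-Meier estimates when progressors exit**

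Let A(t) = exp(-ht) be the progression-free share and B(t) the progressed patients still observed. B(t) is (1 - e) times all living progressors plus e times those who progressed within the last 28 days. The estimated hazard is (dA + qB)/(A + B). Since q exceeds d (by a factor of 6.6 at f = 10% and 2.8 at f = 20%), taking patients out of B lowers this hazard and raises the curve.

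**Results (f = 10% / f = 20%)**

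| Progressors exiting | 12-month OS shown | Bias, points | Median shown, months | Expected deaths seen in 34 by Month 18 |
|---|---|---|---|---|
| 0% | 53.1 / 52.8% | 0 | 12.8 / 12.8 | 22.8 / 22.3 |
| 10% | 54.1 / 53.4% | 1.0 / 0.6 | 13.1 / 13.0 | 21.1 / 20.8 |
| 25% | 55.8 / 54.5% | 2.7 / 1.7 | 13.6 / 13.3 | 18.5 / 18.7 |
| 50% | 59.5 / 56.7% | 6.4 / 3.9 | 14.7 / 14.1 | 14.2 / 15.2 |
| 100% | 74.7 / 65.4% | 21.6 / 12.6 | not reached | 5.7 / 8.2 |

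The standard error of a 12-month proportion with 34 patients and complete follow-up is sqrt(0.53 x 0.47 / 34) = 8.6 points. The bias is therefore 0.2-0.3 standard errors at 25% exit, 0.5-0.7 at 50%, and 1.5-2.5 if all exit.

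**Second set of medians.** Section 6.1 also gives PFS 4.1 and OS 14.7 months (doxorubicin arm of the olaratumab study). The direction is the same: true 12-month OS is 58-59%. If half exit it shows 60-63% with a median of 15.5-16.3 months. If all exit it shows 64-75% and the median is not reached.

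**The case against.** The other side has a good deal of force.
- The weight of the text favours continued follow-up (Sections 8.1.2, 9.4, 9.5 and 11.2.2, the Table 2 note, and the Month 6 to 18 survival contacts).
- The Section 11.6.2.12 phrase sits in a bullet that adds imaging, and the same visit list includes survival status.
- The Section 14.3.10 exit sentence is in the PFS paragraph. It could describe someone who withdraws consent in order to start another therapy, which Section 9.4 allows. It reaches OS only because leaving the study tends to fix the last-contact date.
- The OS rule censors only patients not known to have died, so a known death counts whatever the study status. Section 16.2 has unrelated deaths beyond 30 days captured on a CRF.

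All of this stands, and it limits the point. It does not remove it: the safeguards work only while the site still regards the patient as on study or happens to learn of the death, and that is what the two phrases put in doubt.

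A reader might infer more, and three such readings are not supported:
- *That OS will be biased.* No document figure says how many progressors would be treated as exits, and the prevailing text says none should be.
- *That footnote 15 makes the 28-day contact the last one.* It calls for follow-up within 28 days. Only patients who leave during the follow-up period are given a final visit. The 28-day last contact used above is an assumption.
- *That the plan tests or compares OS with historical medians.* It does not. Section 6.2 says no comparator is needed, and the 20% benchmark in Section 14.3.10 is for response rate.

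**Conclusion.** The contradiction is real and lies in current text. Its consequence is conditional: to the extent that sites treat progression or new therapy as leaving the study and do not learn of later deaths, Kaplan-Meier OS is too high. On the assumptions above, the 12-month estimate is off by about 1 point if 10% of progressors exit, 2-3 points if a quarter do, and 4-6 points with a median 1.3-1.9 months too long if half do. The 13-22 point error with an unreached median belongs only to the extreme case in which every progressor exits, and should not be read as the expected result. The upward direction requires a higher death hazard after progression than before, which held under both pairs of medians in the protocol. OS is a secondary, descriptive endpoint of a single-arm Phase I study, so no test, decision rule or sample size is affected. The wording is worth correcting because the correction is cheap and missed survival contacts may not be recoverable.

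**What to change.** 1. **Sections 9.4, 11.2.2 and Table 4 footnote 15.** State that progression, new sarcoma therapy or an investigator's decision to stop treatment does not end survival follow-up. Survival status continues to Month 18 by visit, telephone or chart review unless consent for it is withdrawn. Bring the Investigator's-discretion withdrawal in Section 11.2.2 into line with the Section 9.4 list.
2. **Section 11.6.2.12.** Make the imaging bullet refer to stopping treatment, not the study. That edit alone would ask for imaging in patients for whom Section 11.2.2 says it is not needed after progression on the combination, so the two passages must be reconciled at the same time.
3. **Section 14.3.10.** Reword the new-therapy sentence so that it applies to PFS only. It now censors on the day of study discontinuation, a date that does not exist for patients who stay on study, so name another, for example the last tumor assessment before the new therapy. State that OS is censored at the date last known alive, and only for consent withdrawal, loss to follow-up or data cut-off.

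The cost is wording edits plus a few telephone or chart checks for progressors at contacts already on the schedule.

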12 METHODS OF ASSIGNMENT OF INTERVENTION

12.1 ALLOCATION OF TREATMENT

The Investigator or designee will record key information on the patient in the eCRF to verify that the patient meets the inclusion/exclusion criteria (Sections 9.2 and 9.3). The Investigator must not prescribe the study drug until the patient's enrollment is approved and the patient has been assigned to a cohort and dose level based on what is needed to complete the cohort (3 or 6 patients or more if there are discontinuations, or the dose group needs to be expanded for a particular reason). The Investigator will then dispense to the patient an adequate number of either the 400 or 600 mg suppository dosage forms to complete the NOX66 monotherapy portion of the study or a treatment cycle with doxorubicin. Each patient number will be used only once, in sequential order within a cohort as noted below.

Cohort 1	Patient Numbers 101-109
Cohort 2	Patient Numbers 201-209
Cohort 3	Patient Numbers 301-309

The patient numbers for the Dose-Expansion Cohort will range from 401-424.

12.2 BLINDING AND UNBLINDING

This is an open label study.

13 DATA COLLECTION AND MANAGEMENT

13.1 METHODS

The Investigator must ensure there will be primary source documentation for all patient data collected as part of the study, and the data will not be recorded directly on to the eCRFs without the availability of such primary documentation, except for cases in which the Sponsor has predetermined that direct data entry into specified pages of the patient's eCRF is appropriate. The source data may include such documents as clinical notes, laboratory result sheets, pathology reports, radiology results, etc., and will be retained in each patient's medical record or research chart. Electronic CRFs will be provided by the Sponsor.

The Investigator will be responsible for the timeliness, completeness, and accuracy of the information entered on the eCRF. The Investigator will provide access to the Medical Monitor or designated Sponsor representative(s) for the periodic review of all study records, source documents among other records for review and inspection to assure accuracy and completeness of the eCRFs. All eCRFs will be 100% source verified against corresponding source documentation (e.g., office and clinical laboratory records) for each patient.

The Sponsor and designated Sponsor representative(s) will maintain frequent contact with each site to assure the study is conducted according to the Protocol and that all data collected are

accurate and complete. Any deficiencies identified by the Sponsor or representative during the study will be communicated to the site for prompt correction.

13.1.1 ELECTRONIC CASE REPORT FORM

All information relative to the study will be recorded on an eCRF to be supplied to the Investigator. Instructions will be provided for the completion of the eCRF. Data corrections will be automatically documented via the electronic data capture (EDC) software's "audit trail."

13.1.2 STORAGE OF DOCUMENTS

The Investigator will retain source documents and all other study related documents for 2 years after the last approval of a marketing application in an International Council for Harmonization (ICH) region or at least 2 years after the formal discontinuation of the clinical development of the investigational product.

13.2 DATA MANAGEMENT

The Sponsor or a designee/CRO will supply eCRFs. An eCRF must be completed for each patient who signs an Informed Consent Form (ICF). All data collected during the study will be recorded in this individual, patient-specific eCRF. Instructions will be provided for the completion of the eCRF. and any corrections made will be automatically documented via the EDC software's "audit trail" as described above.

Completion of the eCRF should be kept current to enable the monitor to review the patient's status throughout the course of the study. All information and other material to be used by patients and investigative staff must use vocabulary and language that are clearly understood. The eCRF will be completed, reviewed, and signed off or e-signed by the Investigator. The Investigator will sign and date the indicated places on the eCRF via the EDC system's electronic signature. These signatures will indicate that the Investigator inspected or reviewed the data on the eCRF, the data queries, and the study site notifications, and agrees with the content.

If a patient is assigned to receive NOX66 and is not treated with study drug, the reason must be recorded on the eCRF.

13.2.1 DATA CODING

Medications will be coded from the WHO Drug Dictionary and medical history and adverse events will be coded using the MedDRA (Version 22 or higher) terminology for System Organ Class and Preferred Term.

13.2.2 DATA VALIDATION

To ensure the quality of clinical data across all patients and study sites, a Clinical Data Management review will be performed on patient data according to specifications given to the CRO. Data will be vetted both electronically and manually for CRFs and the data will be electronically vetted by programmed data rules within the application. Queries generated by rules and raised by reviewers will be generated within the EDC application. During this review, patient data will be checked for consistency, completeness, and any apparent discrepancies.

Data received from external sources such as central laboratories will be reconciled to the clinical database.

A Data Management Plan will be developed to describe all manual and electronic validation checks of the data prior to analysis.

